8.6. Pharmacodynamics

Not Applicable

8.7. Genetics

Not Applicable

8.8. Biomarkers

Not Applicable

8.9. Immunogenicity assessments

Not Applicable

Protocol Version No. 1.0

9. STATISTICAL CONSIDERATIONS

A SAP will be prepared which will include a more technical and detailed description of the statistical analyses described in this section. This section is a summary of the planned statistical analyses of the most important endpoints including primary and key secondary endpoints.

9.1. Statistical Hypotheses

According to WHO product specific guidance (Notes on the Design of Bioequivalence Study: Albendazole; 29 March 2021), albendazole pharmacokinetics in the fed state is highly variable (up to 68% for Cmax and 62% for AUC). Therefore, this study was designed as a replicate cross-over study, to estimate variability more accurately and, if indicated, to widen the acceptance range for Cmax and AUC(0-t) (World Health Organisation, 2021). Considering the same, full replicate study has been planned in line with WHO product specific guidance document and reference-scaled average bioequivalence approach will be used for hypothesis testing.

The null hypothesis to be tested is:

$$H_0: \frac{\left(\mu_T - \mu_R\right)^2}{\sigma_{WR}^2} \ge \theta$$

Versus alternative hypothesis

$$H_1: \frac{\left(\mu_T - \mu_R\right)^2}{\sigma_{WR}^2} < \theta$$

Where: μ_T and μ_R are the means of ln-transformed PK parameters (Cmax and/or AUC) obtained from the BE study for the test and reference products, respectively.

 σ_{WR} is the within-subject standard deviation of the log-transformed values of PK parameter of the reference study intervention.

Testing will be performed at a level of 0.05 and θ is the scaled average BE limit.

The test drug must pass for primary endpoint PK parameters (Cmax and AUC(0-t)) to demonstrate BE to the reference drug. Let σ_{W0} be the regulatory constant (based on 0.80-1.25 geometric mean ratio restriction criteria) and assumed to be 0.294.

a. The 90% confidence interval of GMR of T/R must be contained within [U, L] = exp $[\pm k \cdot s_{WR}]$, which is scale acceptance limit based on k(θ S),

Where $k = \ln(1.25)/\sigma_{W0}$ which is approx. 0.760

U is the upper limit of the acceptance range, L is the lower limit of the acceptance range,

221030

Protocol Version No. 1.0

swR is the within-subject standard deviation of the log-transformed values of PK parameter of the reference study intervention

b. Point estimate of GMR of T/R should be between 80.00 –125.00%.

For the parameters Cmax and AUC(0-t), if the intra-subject CV_W of for the reference study intervention is less than or equal to 0.30 upon trial completion for any of these treatment group, conventional average BE approach with TOST procedure with α =0.05 for each one-sided test will be used to test $0.8 \le GMR \le 1.25$. This is equivalent to requiring that a 90% interval for the true ratio of test to reference geometric means falls entirely within the range of 80.00 to 125.00%. If the intra-subject coefficient of variation (CV_W) of for the reference study intervention is greater than 0.30 upon trial completion, a reference-scaled average bioequivalence approach will be used⁵.

If the intra-subject variability for Cmax and AUC(0-t) following replicate administrations of the comparator product is > 30%. If this is the case the acceptance criteria for Cmax and AUC(0-t) will be widened to a maximum of 69.84–143.19%.

9.2. Multiplicity Adjustment

No multiplicity adjustment is required for this bioequivalence study.

9.3. Analysis sets

TMF-16298784

Analysis Sets	Description
Randomized	All participants assigned to study treatment
Safety set	The safety set will include all randomized participants who receive at
	least 1 dose of study medication. The safety population will be used for
	all analyses of safety data.
PK set	All participants in the Safety set who had at least 1 measurable PK
	assessment (for the purpose of the PK analysis, only those
	participants in this dataset who have evaluable data for one test and
	one reference period will be used).

9.4. Statistical Analysis

9.4.1. General considerations

The pharmacokinetic parameters will be analyzed to evaluate the differences between the test and reference study interventions by applying referenced scaled average bioequivalence approach.

All the statistical analysis will be performed using SAS® Version 9.4 or higher (SAS Institute Inc., USA).

The participants having pharmacokinetic parameters available for 2 reference treatments will be included for calculation of intra-subject variability of reference study intervention.

Descriptive statistics & average bioequivalence analysis will be performed on the

Protocol Version No. 1.0

participants having pharmacokinetic parameters available for at least on test and 1 reference arm.

9.4.2. Primary Endpoint(s)/Estimand(s) Analysis

9.4.2.1. Descriptive statistics

Statistical analysis for primary endpoints will include descriptive statistics for the following pharmacokinetic parameters:

Cmax and AUC(0-t)

Descriptive statistics (N, n, arithmetic mean, 95% CI of arithmetic mean, geometric mean, 95% CI of geometric mean, SD, median, minimum and maximum) will be presented for primary PK parameters.

Average values of Test Study Intervention-T and Reference Study Intervention-R for PK parameters for each participant will be calculated and reported. Descriptive statistics will be calculated and reported for the same data.

Individual values of PK parameters for Test Study Intervention-T (first administration), Test Study Intervention-T (second administration), Reference Study Intervention-R (first administration) and Reference Study Intervention-R (second administration) for each participant will be calculated and reported. Descriptive statistics will be calculated and reported for the same data.

PK parameters will be analyzed to evaluate the differences between the test and reference products by applying SCABE following EMA guidelines in investigation of bioequivalence regarding highly variable drug product (% of CVw >30), otherwise ABE will be applied.

Analysis of Variance (ANOVA) will be used on In-transformed pharmacokinetic parameters Cmax and AUC(0-t) for albendazole or albendazole sulfoxide. The ANOVA model will include participants, period and formulation as fixed effects.

Each analysis of variance will include calculation of ratio of geometric least-squares means and the standard error associated with these ratios. The above statistical analyses will be done using PROC GLM of SAS® procedure. Significance level of 5% (alpha =0.05) will be used for the model.

More technical and detailed description of the statistical analyses will be described in SAP of this study. This section is a summary of the planned statistical analyses of the most important endpoints including primary endpoints.

9.4.2.2. 90% Confidence Interval

90% confidence intervals for the ratio of geometric least squares means between drug formulations will be calculated for ln-transformed data of Cmax and AUC(0-t) for albendazole and albendazole sulfoxide.

9.4.2.3. Ratio analysis

Ratio of geometric least squares means of test and reference formulations will be computed and reported for ln-transformed pharmacokinetic parameters Cmax and AUC(0-t) for albendazole and albendazole sulfoxide.

9.4.2.4. Intra-subject variability

Intra-subject variability of reference study intervention-R will be computed and reported for ln-transformed pharmacokinetic parameters Cmax and AUC(0-t) for albendazole and albendazole sulfoxide.

The existence of outlier subjects that inflate the intra-subject variability will be assessed. In case of such outliers, results will be reported with and without those outliers

9.4.2.5. Missing and non-reportable values

If 1 or more NQ values occur in a profile before the first measurable concentration, they will be assigned a value of zero concentration.

If a single NQ value occurs between measurable concentrations in a profile, the NQ should be omitted (set to missing) in the derivation of pharmacokinetic parameters and statistical analysis.

If 2 or more NQ values occur in succession between measurable concentrations, the values in question will be set to missing. For the derivation of pharmacokinetic parameters, these NQs will be omitted. The NQ values will be set to 0 and the trapezoidal rule will be applied to all the observed data.

NQs which occur after the last measurable concentration will be omitted (set to missing) in the derivation of pharmacokinetic parameters and statistical analysis. Any missing samples (M) concentration value will be disregarded in pharmacokinetic and statistical analysis.

9.4.2.6. Intercurrent event and handling of missing data

The data will be affected by occurrence of the intercurrent event and only data available while the patient is receiving the treatment will be used under while-on treatment policy strategy. Participant level missing data will not be imputed, and available data will be used in the analysis.

Protocol Version No. 1.0

In the case of emesis/vomiting or use of prohibited/rescue medication, the data for that period will not be used for the analysis of PK parameters relating to the primary endpoint using hypothetical strategy.

9.4.2.7. Bioequivalence Criteria

Based on the statistical results of 90% confidence interval for the ratio of the geometric least square means for both ln-transformed pharmacokinetic parameters Cmax and AUC(0-t), conclusion will be drawn for Test Study Intervention-T vs. Reference Study Intervention-R for albendazole with following considerations.

For Cmax and AUC(0-t):

- 1. If within-reference intra-subject CV of ln-transformed Cmax and/or AUC(0-t) ≤ 30% then bioequivalence of the test study intervention with that of the reference study intervention will be concluded, if the 90% confidence interval falls within the acceptance range of 80.00–125.00% for ln-transformed pharmacokinetic parameter Cmax and AUC(0-t).
- 2. If within-reference intra-subject CV of ln-transformed Cmax and/or AUC(0-t) > 30% then Cmax and/or AUC(0-t) limit will be widened using scaled-average-bioequivalence. Under scaled-average-bioequivalence, [U,L] = exp [±k·swR] where U is the upper limit of the acceptance range, L is the lower limit of the acceptance range, k is the regulatory constant set to 0.760 and SwR is the within-subject standard deviation of the ln transformed values of Cmax and/or AUC(0-t) of the reference study intervention.
- 3. If within-reference intra-subject CV of ln-transformed Cmax and/or AUC(0-t) ≥ 50% then Cmax and/or AUC(0-t) bioequivalence limits will be widened to a maximum of 69.84 143.19%.

Bioequivalence of the test study intervention with that of the reference study intervention will be concluded for Cmax and/or AUC(0-t), if both of the following conditions are satisfied:

- The 90% confidence interval for ln-transformed data of Cmax and/or AUC(0-t) falls within the newly widen range [U, L] = $\exp[\pm k \cdot s_{WR}]$, which is based upon the within-subject variability observed for Cmax.
- The geometric least square mean ratio (GMR) of test to reference for Cmax and/or AUC(0-t) falls within the acceptance range of 80.00–125.00%.

Data of metabolite albendazole sulfoxide will be provided as supportive information only.

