6.3.2.8 Bioequivalence criteria

Based on the statistical results of 90% confidence interval for the ratio of the geometric least square means for both ln-transformed pharmacokinetic parameters Cmax and AUC(0-t), conclusion will be drawn for Test Study Intervention-T vs. Reference Study Intervention-R for albendazole with following considerations.

For Cmax and AUC(0-t):

- 1. If within-reference intra-subject CV of ln-transformed Cmax and/or AUC(0-t) \leq 30% then bioequivalence of the test study intervention with that of the reference study intervention will be concluded, if the 90% confidence interval falls within the acceptance range of 80.00–125.00% for ln-transformed pharmacokinetic parameter Cmax and AUC(0-t).
- 2. If within-reference intra-subject CV of ln-transformed Cmax and/or AUC(0-t) > 30% then Cmax and/or AUC(0-t) limit will be widened using scaled-average-bioequivalence. Under scaled-average-bioequivalence, [U,L] = exp [$\pm k \cdot _{SWR}$] where U is the upper limit of the acceptance range, L is the lower limit of the acceptance range, k is the regulatory constant set to 0.760 and S_{WR} is the within-subject standard deviation of the ln transformed values of Cmax and/or AUC(0-t) of the reference study intervention.
- 3. If within-reference intra-subject CV of ln-transformed Cmax and/or AUC(0-t) \geq 50% then Cmax and/or AUC(0-t) bioequivalence limits will be widened to a maximum of 69.84 143.19%.

Bioequivalence of the test study intervention with that of the reference study intervention will be concluded for Cmax and AUC(0-t), if both of the following conditions are satisfied:

- The 90% confidence interval for ln-transformed data of Cmax and AUC(0-t) falls within the respective newly widen range [U, L] = $\exp\left[\pm k \cdot _{SWR}\right]$, which is based upon the within-subject variability observed for respective pharmacokinetic parameter.
- The geometric least square mean ratio (GMR) of test to reference for Cmax and AUC(0-t) falls within the acceptance range of 80.00–125.00%.

Data of metabolite albendazole sulfoxide will be provided as supportive information only.

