A list of all protocol deviations and an assessment of their impact will be included in listing. The deviations will include dosing related, IMP related, lab related, early, late or missed safety assessments, etc.

A number of participants with minor and major deviations will be provided.

8 Change from the protocol

"The ANOVA model will include sequence, participant(sequence), period and formulation as fixed effects" as per the WHO requirements.

9 Interim analysis

No interim analysis has been planned in this study.

[figure not shown]
10 Software Information for Analysis

SAS® Version 9.4 or higher (SAS Institute Inc., USA) will be used for statistical and safety analysis.

Phoenix® WinNonlin® Version 8.3 or higher (Certara L.P.) will be used for pharmacokinetic analysis.

11 Format Specifications for outputs

1. Output files of SAS procedures/Phoenix WinNonlin (statistical analyses, summary tables, individual data listings, etc.) will be produced as PDF files.

Project No. 0110-23 Version 00

- 2. Each individual PDF file will contain the statistical analysis output, i.e. a summary table, or data listing grouped by treatment or/and visit, for one analysis population, and for a single type of analysis.
- 3. The rules for grouping may vary according to the type of data (study outcome, safety), individual data listings, listings of derived variables, etc. and the type of output file which is produced (statistical analyses, summary tables, graphs).
- 4. Page format will be "A4".
- 5. Each listing will be numbered in the format Page X of Y (where Y denotes total number of pages in that particular listing). Page number will appear in the bottom right part of the listing.
- 6. For each output, 'Lambda Therapeutic Research Ltd.' Will appear in the Top left corner of the Header, 'Confidential' and 'Title' of the output will appear in the Centre of the Header and towards the Top right corner the 'project number' will be presented.
- 7. The font and font size for header/footer and body of the output will be Courier New size 9 pt which will be generated from SAS. The font and font size for header/footer and body of the output will be Times New Roman 12 pt which will be generated from Phoenix WinNonlin.

12 List of Tables

14.1	Demographic data
14.1.1	Demographic data and baseline characteristics (Randomized set)
14.1.2	Demographic data and baseline characteristics (Safety set)
14.1.3	Demographic data and baseline characteristics (PK set)

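### Protocol 9.4.2.7 takes the AUC(0-t) limits from Cmax variability, the SAP differs without listing the change, and neither document says which rule governs if the two reference CVs straddle 30%

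*Protocol*

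**What the plan says.** **Source of the widened limits.** The closing conditions of protocol 9.4.2.7 cover Cmax and AUC(0-t) and use a range "which is based upon the within-subject variability observed for Cmax". Rule 2 of the same section says that sWR "is the within-subject standard deviation of the ln transformed values of Cmax and/or AUC(0-t) of the reference study intervention". Protocol 9.1 defines it as the "within-subject standard deviation of the log-transformed values of PK parameter of the reference study intervention". SAP 6.3.2.8 uses a range "which is based upon the within-subject variability observed for respective pharmacokinetic parameter", and replaces 'and/or' by 'and' in the closing conditions.

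**Record of changes.** SAP section 8 lists one change from the protocol: "The ANOVA model will include sequence, participant(sequence), period and formulation as fixed effects". The protocol does leave detail to the SAP (section 9: "A SAP will be prepared which will include a more technical and detailed description of the statistical analyses described in this section").

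**Rules 1 and 2.** The two documents word these alike. Rule 1 is triggered when the reference CV of Cmax 'and/or' AUC(0-t) is at or below 30%. Bioequivalence is then concluded "if the 90% confidence interval falls within the acceptance range of 80.00–125.00% for ln-transformed pharmacokinetic parameter Cmax and AUC(0-t"). Rule 2 is triggered when the CV of Cmax 'and/or' AUC(0-t) exceeds 30%, "then Cmax and/or AUC(0-t) limit will be widened using scaled-average-bioequivalence". Rule 3 caps the widening at 69.84–143.19% from a CV of 50%.

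**The concern.** These sentences set the primary acceptance limits, and the limits depend on CVs observed at the end of the trial. They should have one reading before those CVs are known. There are two gaps.

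- The protocol and the SAP state different limits for AUC(0-t), and the record of changes does not show it. Limits taken from Cmax are too wide for AUC(0-t) if Cmax is the more variable parameter, and too narrow if it is the less variable one. The two sets of limits coincide once both CVs reach the 50% cap.
- If one reference CV is at or below 30% and the other is above it, rules 1 and 2 are both triggered. On a strict reading rule 1 holds both parameters to 80.00–125.00%, while rule 2 widens one of them. The study is open label, so choosing between the readings after the CVs are known would be a data-dependent choice of the primary limits.

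**Working it through.** **1. The documents' limits reproduce.** With sWR = √ln(1+CV²) and limits exp(±0.760·sWR):

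- k = ln(1.25)/0.294 = 0.2231/0.294 = 0.759, which the documents round to 0.760.
- CV 30%: sWR 0.2936, limits 80.00–125.00%.
- CV 35%: sWR 0.3399, limits 77.23–129.48%.
- CV 40%: sWR 0.3853, limits 74.62–134.02%.
- CV 48%: sWR 0.4554, limits 70.75–141.35%.
- CV 50%: sWR 0.4724, limits 69.84–143.19%, the stated cap.

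At 68/62 both parameters normally sit at the cap. At 48/48 the true limits are equal. So Cmax-based and own-parameter limits should barely differ at either planning scenario.

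**2. Simulation set-up.** There were 60,000 trials per scenario (Monte Carlo SE at most 0.2 points).

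- From the documents: TRTR/RTRT, 48 completers (24 per sequence), T/R ratio 0.90 unless stated, 90% CI, rules 1–3, GMR within 80.00–125.00%.
- Analysis: fixed subject, period and formulation effects, residual df = 192 − 48 − 3 − 1 = 140. sWR comes from the two reference periods within sequence, 46 df.
- Assumed: equal within-subject variance for test and reference, and a within-subject Cmax/AUC correlation of 0.685/√(0.814 × 0.747) = 0.878 from Table 10.

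CVs below are Cmax/AUC(0-t).

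**3. Planning CVs (protocol 9.6).** Joint power on own limits against Cmax-based limits is 92.5% v 92.6% (48/48) and 86.1% v 86.2% (68/62). Observed CVs straddle 30% in at most about 0.03% of trials, so rule 1 has no visible effect.

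**4. Cmax-based limits (protocol text only).** The CV pairs are assumed for illustration.

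| CVs | Quantity | Own limits | Cmax-based limits |
|---|---|---|---|
| 50/35, true AUC ratio 0.772 | AUC pass rate | about 6% | about 23% |
| 50/40, true AUC ratio 0.746 | AUC pass rate | about 5% | about 10% |
| 35/50 | joint power | about 89% | about 71% |
| 40/50 | joint power | about 91% | about 83% |

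The ratios 0.772 and 0.746 are AUC's own lower limits at CV 35% and 40% (step 1). Own limits give slightly more than 5% because sWR is estimated.

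**5. Rule 1 read strictly (both documents).** The CV pairs are again assumed. The comparison is per-parameter limits against 80.00–125.00% for both parameters whenever either observed CV is at or below 30%.

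| CVs | Trials straddling 30% | Joint power, per parameter | Joint power, strict rule 1 |
|---|---|---|---|
| 40/48 | about 1% | 91.5% | 91.4% |
| 32/48 | about 30% | about 89% | about 81% |
| 28/48 | about 77% | about 90% | about 65% |
| 48/25 | about 97% | about 93% | about 57% |

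**6. Calibration.** For 48 completers Table 11 gives 90.3% and 93.7%; this model gives 92.5% and 86.1%. Exchanging 68 and 62, as the header of Table 11 does, leaves 86.1%. Removing the cap gives 88.2%. Neither closes the gap.

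**The case against.** The strongest reply has four parts.

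- **The SAP already cures the Cmax-only rule.** The protocol hands detail to the SAP, SAP 6.3.2.8 uses the respective parameter, and the shell of SAP Table 14.2.1.1 reports reference CV and sWR in separate columns for Cmax and AUC(0-t). This stands. The figures in step 4 describe the protocol text, not the analysis that the SAP would run. What remains is two documents that disagree and a change that is not recorded.
- **The collision needs a strict reading.** Rule 2 can be read parameter by parameter. Protocol 9.1 defines sWR by parameter. Protocol 9.4.2.1 and SAP 6.3.2.1 apply scaling to parameters with CV above 30% and ordinary average bioequivalence otherwise. Rule 1 says 'if', not 'only if'. This largely stands: the per-parameter reading is probably intended. But rule 1 still names both parameters in both documents, and no precedence is stated. The sentences on the 30% threshold in protocol 9.1 and SAP 6.1 refer to treatment groups and do not settle it.
- **The CV pairs are hypothetical.** This stands. The documents give 68/62 and 48/48, and describe in-house data as closer to 48%. With their largest gap of 6 points placed around 48%, strict rule 1 changes nothing material: 92.0% v 91.9% at 48/42 and 92.1% v 92.1% at 42/48. The 48/25 case needs an AUC CV about half the lowest planning value.
- **The correlation is uncertain.** Read as within-subject log variances, the Table 10 values imply CVs of √(e^0.814 − 1) = 112% and √(e^0.747 − 1) = 105%, which match neither scenario. So 0.878 has no documented status as a within-subject correlation. A value of 0.3 gives 90.3% at 48/48, Table 11's figure. It barely changes the 48/25 gap.

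A reader might also infer from 'and/or' in the protocol's closing conditions that one passing parameter is enough. The documents do not support that. Protocol 9.1, the opening sentence of 9.4.2.7, the joint-power design in 4.2 and 9.6, and the SAP all require both.

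**Conclusion.** The limits are wrong as written in the protocol and incompletely specified in both documents, with low practical impact at the planning CVs: about 0.1 point of joint power, and straddling in at most about 0.03% of trials. The sample size of 48 evaluable and 70 enrolled does not depend on it.

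Two stronger conclusions are tempting. One is that AUC(0-t) will in fact be judged on Cmax variability; the SAP says otherwise. The other is that the trial loses power whenever a CV falls to 30% or below; that holds only if rule 1 is read strictly and the other CV stays above 30%.

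The larger effects in steps 4 and 5 rest on assumed CV pairs, an assumed within-subject correlation and a model that does not reproduce Table 11. They show direction and rough size only. The point still merits correction: the limits follow the observed CVs rather than the planning values, so every branch of the rule needs one meaning in advance.

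**What to change.** In protocol 9.1 and 9.4.2.7 and SAP 6.1 and 6.3.2.8, state the rule once for each of Cmax and AUC(0-t), on that parameter's own reference CV:

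- CV ≤ 30%: 90% CI within 80.00–125.00%.
- CV > 30% and < 50%: 90% CI within exp(±0.760·sWR), with that parameter's sWR.
- CV ≥ 50%: 90% CI within 69.84–143.19%.
- GMR within 80.00–125.00%.
- Bioequivalence concluded only if both parameters pass.

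Delete the Cmax-only phrase, 'and/or', and the reference to treatment groups in the sentences on the 30% threshold in protocol 9.1 and SAP 6.1. List the change in SAP section 8 before database lock.

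The cost is wording only: a protocol amendment or note and a SAP revision. There is no operational cost and no change to the sample size.
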